2. Protocol Registration:**3. Protocol version:****4. Funding:**

No Sources of Funding to be declared

5. Roles and responsibilities:**Main Supervisor:**

[name]

BDS, MOrthRCSEd, MSc, PhD, FDSRCSEd

Co-supervisor:

[name] [name],

DDS - MSc – PhD - M.OrthRCSEd – FDSRCSEd (UK)

Lecturer of Orthodontics & Dentofacial Orthopedics Cairo University

Responsible for development of research opinion

II. Introduction:

6. Background and rationale:

It was introduced in dentistry to be used in innovative research and development in addition to facilitating the decision in complicated cases and ensure high patient care quality. In the field of Orthodontics in specific, many studies previously mentioned the idea of artificial intelligence showing very promising results and high degree of reliability. It was used in different domains in orthodontics like diagnosis, treatment planning, evaluation of treatment outcome. In this study, the aim is to access the efficiency of the new decision support system in determining whether the decision is extraction or non-extraction and the anchorage plan required for each case. This was performed in the past in many countries and those studies are published (Will be discussed later in the literature review section)

Research question: Will the computer Algorithm be efficient in producing decisions related to extraction, non-extraction and anchorage planning?

Rationale:

This study will help the orthodontists in making the correct decisions regarding the extraction and anchorage based on clinical data acquired from the patient. Different papers were published to illustrate the previously mentioned concept but with different accuracies. So, this study is testing how efficient this system will be in an attempt to reach high level of efficiency.

Intended use of the index test:

This Index test is intended to be used in extraction/ non-extraction decision and anchorage planning.

Clinical role of the index test:

This index test will be under evaluation aiming to assess the efficiency of newly formed decision support system concerning extraction and anchorage planning in non-growing patients compared to the clinician-based treatment planning of well- finished cases.

Review of literature:

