3) Jung and Kim, 2016^[17], study was targeting to construct an artificial intelligence expert system for the diagnosis of extractions using neural network machine learning and to evaluate the performance of this model, 156 patients were included in the study. The success rates of the models were 93% for the diagnosis of extraction versus non-extraction and 84% for the detailed diagnosis of the extraction patterns.

4) Thanathornwong, 2018^[41] assessed the need for orthodontic treatment using Bayesian-Based Decision Support System. The Bayesian decision support module consisted of relevant variables taken from treatment need indexes (IOTN, ICON, and DAI). These three indexes referred to the same variables focusing on anterior teeth, including overbite, anterior open-bite, diastema, anterior crossbite, anterior displacement, and anterior-posterior molar relationship. The proposed decision support system was evaluated by a comparison of the orthodontic treatment needs assessed by orthodontists with those assessed by the system. It achieved a high degree of accuracy in classifying patients into groups needing and not needing orthodontic treatment.

5) Artificial Neural Networks (ANN) are used by Li *et al.*, 2019^[22] to predict orthodontic treatment plans, including the determination of extraction and non-extraction, extraction patterns, and anchorage patterns. The accuracies of the extraction patterns and anchorage patterns are 84.2% and 92.8%. Since anchorage is important to reach target of extraction and maximum use of the extracted space. This article discussed the highest contributing factors in anchorage planning like curve of spee, Nasolabial angle, UL-EP

6) In 2020, Suhail *et al.*,^[40] An expert system was developed that is able to reach suitable treatment decisions that can be valuable to clinicians for verifying treatment plans, minimizing human error, training orthodontists, and improving reliability. A number of machine learning models for this prediction task using data for 287 patients was evaluated independently by five different orthodontists. The benefits of this study that it does not only focus on this binary decision but also which specific tooth/teeth requiring extraction.

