- (4) Detailed documentation of the treatment sequence and mechanics. If there were incomplete data provided in the patient's file; the patient will then be excluded from the study.

11. Where and when potentially eligible participants will be identified (setting,

location and dates)

Recruiting patients from Ksar El Ainy – Cairo University, future university archive with their specific eligibility criteria once the paper work is approved

12. Whether participants formed a consecutive, random or convenience series:

Any Patient that passes the inclusion criteria in terms of file including patient full records, Mechanics used were well registered and the case was well finished based on that the patient will be enrolled.

No subdivisions will be done

C) Test method:**13. Index test & reference standard in sufficient detail to allow replication**

A- The Preanalytical Phase:

Patients should have finished their orthodontic department at Cairo University with full Records available

B- The Analytical Phase:

Experts will analyze the outcome resulting from decision support system regarding extraction or non-extraction and anchorage planning and whether it is comparable to those conventional decisions reached by the orthodontic clinicians during treatment planning

C- Postanalytical Phase: Calculation of the efficiency of the system

14. Rationale for choosing the reference standard

Conventional Decisions (Decisions made by Orthodontic Clinicians) concerning extraction or non-extraction and anchorage planning for well finished cases

15. Definition and rationale for test positivity cut-offs of the index test & reference standard:

The study will test the efficiency of the decision support system according to those by the Orthodontic Clinicians

16 a. Clinical information and reference standard results will be available to the performers of the index test

Index test performers will be blinded

16 b. Clinical information and index test results will be available to the assessors of the reference standard

The assessors will be blinded from the treatment mechanics and results

D) Statistical analysis

17. Methods for estimating or comparing measures of diagnostic accuracy

Co-relation analysis will be used to compare the outcomes of both methods (conventional & computerized)

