Statistical analyses will be performed using SPSS (version 22.0; IBM Corp, Armonk, NY). More than 1 type of statistical analysis will be used to address the outcomes. Cohen's kappa coefficient will be used to measure the agreement between the 2 methods on the basis of choice of the same options without consideration of the value assigned to each option (qualitative data). If a value were assigned to the option, it would be given 1, and if it were not assigned, it would be given 0. Cohen's kappa coefficient is a more robust method than simple percentage agreement, and its value dictates the strength of agreement (<0.20, poor; 0.21-0.40, fair; 0.41-0.60, moderate; 0.61-0.80, good; and 0.81-1.00, very good).

The concordance correlation coefficient would be used to measure the agreement between the 2 methods on the basis of the values (%) assigned for each treatment option by the 2 methods (quantitative data).

A value of ≥ 1 , corresponds to perfect agreement; ≥ 0.8 , very good; ≥ 0.7 , good; ≥ 0.5 , moderate, ≥ 0.4 , fair; ≥ 0.3 , poor; and 0, no agreement.

The sum of absolute difference and the relative sum of absolute difference were used to measure the percent error between the 2 methods on the basis of the values assigned for each treatment option (quantitative data).

18. How indeterminate index test or reference standard results will be handled:

It is not applicable as the outcome will be based on decisions made by the program

19. How missing data on the index test and reference standard will be handled

Any Patient file with incomplete data will not be included from the beginning in the study

20. Sample size calculation and how it was determined

Sample size is being calculated and waiting for approval

IV. Ethics and dissemination**21. Research ethics approval**

This protocol will be reviewed by the Ethics Committee of Scientific Research –Faculty of Oral and Dental Medicine Cairo University

22. Protocol amendments

Any modification to the protocol which may have an impact on the conduct of the study, potential benefit of the patient or may affect patient safety will require a formal amendment to the protocol. Such amendment will be agreed upon by the Council of orthodontic Department.

23. Informed consent

Template will be reviewed by the Ethical committee and will be signed by the patients or their legal guardians

24. Confidentiality

All study-related information will be stored securely by the personnel conducting the study

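### Section 17 grades the extraction and anchorage decisions on kappa alone, which shifts with case mix and is 0 or undefined for extraction under the eligibility criteria as written

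*Protocol*

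**What the plan says.** Protocol section III.D.17 is headed "Methods for estimating or comparing measures of diagnostic accuracy". For the qualitative decisions it states: "Cohen's kappa coefficient will be used to measure the agreement between the 2 methods on the basis of choice of the same options". It justifies this choice by saying "Cohen's kappa coefficient is a more robust method than simple percentage agreement", adds that "its value dictates the strength of agreement", and gives the bands "<0.20, poor; 0.21-0.40, fair; 0.41-0.60, moderate; 0.61-0.80, good; and 0.81-1.00, very good".

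The other measures in section 17 are an unspecified correlation analysis, a concordance correlation coefficient, and absolute-difference measures: "The sum of absolute difference and the relative sum of absolute difference were used to measure the percent error between the 2 methods". The concordance coefficient and the absolute differences apply to percentage values assigned to treatment options, not to whether a decision matched. No match rate, accuracy, sensitivity or specificity against the clinician reference is listed.

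Two other places bear on this:

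- Section II.6 (Rationale) describes earlier work by its accuracy: "Different papers were published to illustrate the previously mentioned concept but with different accuracies". The literature review then cites extraction and anchorage systems by accuracy or success rate (80%, 84%, 84.2%, 91%, 92.8%, 93%).
- Section III.B.9 (Eligibility criteria) includes cases with crowding above 10 mm that needed extraction, and excludes mild crowding treated by other means. Section 7 nevertheless has the extraction/non-extraction decision as an objective.

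**The concern.** Kappa compares observed agreement with the agreement expected from the marginal frequencies. When one decision dominates, expected agreement is high and kappa can be low even though the program matches the clinician in most cases. A plan that turns kappa directly into a verbal grade, without showing the match rate or the marginals, can therefore give the same match rate different grades in different archives. The reader would have no means of telling a weak program from a skewed case mix.

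Here the case mix is restricted by design. If nearly every reference decision is extraction, the extraction kappa says almost nothing about the program, yet it would still be graded.

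**Working it through.** The protocol gives no sample size, expected kappa or case mix, so there is no figure of its own to reproduce. The match rate of 92.8% is the anchorage accuracy cited in the literature review, used only as an illustration. All class shares below are assumptions.

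**Formula.** kappa = (Po − Pe)/(1 − Pe), where Po is observed agreement and Pe is agreement expected from the marginals.

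**Two classes, same marginals for program and clinician.** Pe = m² + (1 − m)², where m is the share of the main class and Po = 0.928.

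| Split | Pe | kappa | Plan's band |
|---|---|---|---|
| 50/50 | 0.500 | 0.428/0.500 = 0.856 | very good |
| 80/20 | 0.680 | 0.248/0.320 = 0.775 | good |
| 90/10 | 0.820 | 0.108/0.180 = 0.600 | moderate |
| 95/5 | 0.905 | 0.023/0.095 = 0.242 | fair |

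**Two classes, sensitivity = specificity = 0.928.** At 95/5 the program names the main class in 0.95 × 0.928 + 0.05 × 0.072 = 0.8852 of cases. Pe = 0.95 × 0.8852 + 0.05 × 0.1148 = 0.84668, and kappa = 0.08132/0.15332 = 0.53 (*moderate*). The fall is smaller but still crosses two bands from the 0.856 at 50/50.

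**Three classes.** Each reference class is matched in 92.8% of its cases, with the errors split equally over the other two.

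- Balanced: Pe = 1/3, kappa = 0.5947/0.6667 = 0.89 (*very good*).
- 90/8/2: the program's marginals are 0.8388, 0.10736 and 0.05384. Pe = 0.9 × 0.8388 + 0.08 × 0.10736 + 0.02 × 0.05384 = 0.7646, and kappa = 0.1634/0.2354 = 0.69 (*good*).

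**Extraction decision, eligibility read literally.** All reference decisions are extraction. If the program says extraction in a share q of cases, Po = q and Pe = 1 × q + 0 × (1 − q) = q. Then kappa = (q − q)/(1 − q) = 0 for every q below 1, and 0/0 at q = 1. A 93% match would be graded *poor*, and so would a 50% match.

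**Reverse direction.** With sensitivity equal to specificity, kappa 0.60 corresponds to 80% agreement at 50/50, 90.3% at 90/10 and 94.4% at 95/5. A kappa reported without marginals cannot be turned back into a match rate.

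**The case against.** - **Preferring kappa is defensible.** At 95/5 a program that always names the main class is 95% correct, which beats 92.8%, so a kappa of 0.24 is a fair warning. This stands: much of the fall is intended. It does not justify grading on kappa alone, and it does not help where the reference has only one category.
- **The skewed tables are assumed.** The anchorage classifications in the literature review have three or four levels, and no case mix is given. With three classes the example moves only from *very good* to *good*. Section 17 also codes each option 1 or 0. If kappa were pooled over three options with one chosen per case, each wrong case would spoil two of three cells: Po = 1 − 0.072 × 2/3 = 0.952, Pe = (1/3)² + (2/3)² = 5/9, and kappa = 0.89 whatever the class mix. That is one possible reading, which the protocol does not fix. The anchorage effect is therefore uncertain in size.
- **The match rate comes from the same table and is not forbidden.** This is true, and an analysis plan may add rows. But the protocol itself chooses the measure and fixes how it is graded, so the grading rule is more than a detail left for later.
- **Percentage match has the same weakness under this eligibility.** Always answering extraction would score 100%. This stands, and is why eligibility has to be reconciled as well.

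A reader might also infer that the cited accuracies are the trial's benchmarks and that using kappa defeats a planned comparison with them. The protocol does not support that. Its hypothesis is agreement with the orthodontist; it sets no target accuracy and plans no comparison with published systems. Populations differ too: one cited system was built on patients aged 11 to 15, whereas this study excludes growing patients. Percentages side by side would not rank the systems.

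**Conclusion.** The concern holds as a defect of grading and reporting. Kappa is the only specific measure for the categorical decisions, and its value alone sets the grade, under a heading about diagnostic accuracy that is followed by no accuracy measure for those decisions.

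For extraction, the result needs no assumed case mix, only a literal reading of section 9: kappa is 0 or undefined whatever the match rate. For anchorage, the size depends on an unknown case mix and on how the 1/0 coding is used. At 92.8% agreement the assumed tables run from 0.86 to 0.24 with two classes and from 0.89 to 0.69 with three.

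The documents do not show that kappa is the wrong statistic, that its stated advantage over raw agreement is false in general, or that the study fails a promised comparison with earlier systems.

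**What to change.** In section 17, for each decision:

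1. Report the full program-by-clinician cross-tabulation with its marginals.
2. Report the percentage match with an exact or Wilson 95% interval.
3. Report the match rate within each reference category, which exposes a program that always gives the same answer.
4. Report kappa beside these, and do not grade agreement on the kappa band alone. State whether kappa is computed per option, pooled over options or on the multi-class table.
5. Keep the sentence preferring kappa to simple percentage agreement, but qualify it for a skewed case mix.

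The percentages may be shown descriptively next to the accuracies cited in section II.6, without a ranking.

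Separately, reconcile the eligibility criteria in section 9 with the extraction/non-extraction objective in section 7. While the reference holds one category only, neither kappa nor percentage match can show whether the program separates the two decisions.

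Items 1 to 5 cost a few more rows in the results table, from data already tabulated for kappa. The cost of reconciling sections 7 and 9 depends on which of them the investigators change.

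### The concordance and absolute-difference measures need clinician percentages for each option, but the reference is a recorded clinical decision and the plan gives no source for percentages

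*Protocol*

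**What the plan says.** Section III.D, item 17 compares two methods, conventional and computerized, with three kinds of measure:

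- Kappa, "on the basis of choice of the same options without consideration of the value assigned to each option", where an option is coded 1 if a value was assigned to it and 0 if not.
- A CCC, "on the basis of the values (%) assigned for each treatment option by the 2 methods (quantitative data", graded from poor to perfect.
- Absolute differences: "The sum of absolute difference and the relative sum of absolute difference were used to measure the percent error between the 2 methods", again on the values given to each option.

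The conventional side is fixed elsewhere. Section III.A, item 8 takes the data from the archives of two universities. Section III.C, item 14 names the reference as "Conventional Decisions (Decisions made by Orthodontic Clinicians) concerning extraction or non-extraction and anchorage planning for well finished cases", and item 13 places these as "conventional decisions reached by the orthodontic clinicians during treatment planning". Section III.B, item 10 lists what each file must hold: x-rays, photographs, study models and "Detailed documentation of the treatment sequence and mechanics".

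Three further items touch the point. Item 13 has experts examine the system's output and judge whether it is comparable with the conventional decisions. Item 16b says of those who assess the reference standard: "The assessors will be blinded from the treatment mechanics and results". Item 18, on indeterminate results, answers: "It is not applicable as the outcome will be based on decisions made by the program".

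**The concern.** The CCC and the absolute differences need a percentage for every option from both methods. The reference described in items 8, 10, 13 and 14 is a choice among categories, made during past treatment planning. The listed file contents hold no percentages, and neither the experts nor the assessors are asked to produce any. The only coding rule in the document reduces an assigned value to 1 or 0 for kappa. It presupposes values and does not create them.

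The hypothesis in section II.7 is that the program's decisions match the orthodontist's. If a coding is chosen later, that choice determines whether the graded measures repeat kappa or describe something other than agreement on the decision.

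**Working it through.** The protocol states no sample size, number of options or expected agreement, so it has no figure to reproduce. The calculation below uses assumed inputs to show what the CCC would measure under the two obvious codings.

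**Formula.** CCC = 2·cov / (var_x + var_y + (mean_x − mean_y)²), with variances on divisor n.

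**Coding A: clinician 100/0, program graded.** Assume two options, rows pooled over options, and a program that always favours the clinician's option, giving it p% and the other (100 − p)%.

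- Clinician rows: mean 50, variance 2500, whatever the share of extraction cases, because each case adds one 100 and one 0.
- Program rows: mean 50, variance (p − 50)². Covariance: 50(p − 50).
- CCC = 100(p − 50) / (2500 + (p − 50)²).
- Sum of absolute differences per case = 2(100 − p) points.

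| p | CCC | Sum of absolute differences |
|---|---|---|
| 60 | 1000/2600 = 0.385 | 80 |
| 70 | 2000/2900 = 0.690 | 60 |
| 80 | 3000/3400 = 0.882 | 40 |
| 90 | 4000/4100 = 0.976 | 20 |
| 100 | 5000/5000 = 1.000 | 0 |

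The decisions agree in every case in every row of the table. On the protocol's own bands the label still moves from poor (0.385) through moderate (0.690) and very good (0.882) to perfect. With three options and balanced classes the same check gives 0.47 at 50% on the top option, 0.69 at 60% and 0.85 at 70%.

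For contrast, take a program that outputs 100/0 and errs in a share e of cases. Both variances are 2500 and the covariance is 2500(1 − 2e), so CCC = 1 − 2e. At e = 0.10 this is 0.80, with 200 × 0.10 = 20 points per case. That program is wrong in one case in ten, yet its CCC is above that of an always-right program at 60/40 or 70/30, and below that of one at 80/20 or higher.

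**Coding B: both methods 0/100.** Let p1 and p2 be the two methods' shares of rows coded 100, and p11 the share coded 100 by both. Rescale to 0/1:

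- CCC: the numerator is 2(p11 − p1·p2). The denominator is p1(1 − p1) + p2(1 − p2) + (p1 − p2)² = p1 + p2 − 2·p1·p2.
- Kappa: observed minus chance agreement is 2(p11 − p1·p2), and one minus chance agreement is p1 + p2 − 2·p1·p2.

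The two are identical on the same rows. With two options the summed absolute difference is 200e, which restates the error rate.

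**Extraction row alone.** Inclusion criterion 2 (section III.B, item 9) admits cases requiring extraction. If every reference decision is extraction, p1 = 1 and p11 = p2, so kappa has numerator 0 and denominator 1 − p2. It is 0 if the program errs at all and undefined if it never does. The CCC has zero covariance there too.

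**The case against.** The strongest objection is that the percentages might come from a fresh rating. Item 17 speaks of values assigned by both methods. Item 16b blinds the reference assessors to mechanics and results, which fits a new rating better than copying a recorded decision. A scoring form or an unseen SAP could then supply the detail. This stands in part. A reader might infer that the measures cannot be computed at all, and the document does not support that. What it supports is that the source of the percentages is undefined: item 14 keeps the clinicians' own decisions as the reference, and no rating task is written for anyone. An SAP could impose a coding, but it cannot recover percentages that the files do not hold, and new ratings are a data-collection step.

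A second objection is that 60/40 is the unfavourable end. That is right, so the whole range is shown. Absolute difference against a 100/0 reference is also a meaningful error measure for graded output, but it answers a different question from agreement of decisions.

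Two further inferences are tempting and should not be drawn:

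- **The kappa rule is itself wrong.** It would penalise an always-right program only if any non-zero value counts as 1 and the clinician side is a single choice. If both sides spread values over options, the rule is coherent. The wording needs clarifying, but no error is shown.
- **The differing grade bands for kappa and CCC are an error.** They would label one number in two ways only if both methods were coded 0/100, which the protocol does not adopt.

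Item 18's reference to program decisions is also weak evidence on output format, since it answers a question about indeterminate results.

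**Conclusion.** The concern holds in this form: the protocol fixes two graded measures on percentages while fixing a reference that is a categorical decision, with no stated route from one to the other. Under 100/0 coding against graded output, the CCC reflects how extreme the program's percentages are, from 0.39 to 1.00 for a program that is never wrong. Under 0/100 coding for both, it duplicates kappa. These figures assume two options and pooled rows, neither of which the protocol states. The algebraic identity in the second case needs no such assumption.

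The change should be made, but the defect does not undermine the whole study. No passage makes the CCC primary, and kappa on the chosen category can still address the hypothesis for anchorage. For extraction, kappa is uninformative while inclusion is limited to cases requiring extraction.

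**What to change.** Drop the CCC and the sum and relative sum of absolute differences for treatment options, and in their place:

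- Compare the program's top choice with the clinician's recorded decision by percent agreement with a confidence interval, separately for extraction and for anchorage.
- Add kappa for anchorage. For extraction, rely on percent agreement under the present inclusion criterion, and say that it then describes agreement in extraction cases only.
- State that 1 in the kappa rule means the option chosen.
- Use one stated list of anchorage categories. The literature review cites a scheme of four classes and one of three groups, and the methods name none. Abstract the category from the file blind to program output.

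The cost is protocol wording, a small change to the analysis code and a small abstraction step. The required contents list mechanics rather than an anchorage category. However, exclusion criterion 6 (patients who did not keep to the anchorage plan) presupposes that a plan can be identified for each case. The downside is that the graded summary is lost.

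If the percentage measures are to stay, the protocol must say who assigns the clinician percentages, by what rule, and that this is done blind to program output. That means new clinician ratings.
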